	
Optimal dosage and conditions, as well as possible mechanisms of action for IH remain unclear. Adequately powered randomized, controlled trials are required to confirm whether IH is viable as a longer-term treatment option for obesity and the associated comorbidities.
 
This proposed novel research addresses functional and medical concerns following SCI. The purpose of this proposal is to examine changes in glycemic control and metabolism while at rest and during exercise after 5 days of resting exposure to AIH when compared with a time-matched normoxia (SHAM) treatment.

5.	Inclusion and Exclusion Criteria
	
Screening: Subject candidates will be pre-screened by phone or personal contact to determine their eligibility based upon age and body habitus (i.e., height/weight). Subjects with SCI and non-injured control (CON) subjects will be recruited.
 
Inclusion Criteria:
 
 a. Males and females aged 18-60 years. b. SCI only: 
 1. Lower extremity weakness or paralysis at C5 or below resulting from spinal cord injury for at least one year. 2. ASIA Classification A-D c. Overweight or obese as classified by a Body Mass Index (BMI) (kg/m^2) of ≥ 25.0 (CON) and ≥ 22.0 (SCI). d. Resting $\text{SaO}_2 \geq 95\%$ 
Exclusion Criteria SCI and CON:
 
 a. Currently hospitalized b. Resting heart rate ≥ 120 BPM c. Resting systolic blood pressure > 180 mm Hg d. Resting diastolic Blood Pressure > 100 mmHg e. Self-reported history of unstable angina or myocardial infarction within the previous month f. Previous cardiac surgery or condition that evidences ischemic heart disease g. Cardiopulmonary complication such as COPD h. Pregnancy determined by urine testing in sexually active females.
6.	Number of Subjects
	Total target accrual is N= 20; 10 SCI and 10 CON.
7.	Study-Wide Recruitment Methods

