	
General
 
Participant Burden:
 
 The informed consent process and screening will require approximately 30 minutes. The oral glucose tolerance test will take 2 hours plus 15 minutes of preparation time and 15 minutes to achieve post-treatment homeostasis. Graded exercise testing will require approximately 60 minutes. AIH and SHAM exposures will be administered on 4 consecutive days for approximately 60 minutes each day. 
Research Design: A mixed models repeated measures (time) design examining metabolism and dysglycemia for subjects undergoing 2 treatment conditions (AIH and SHAM).
 
Protocol:
 
 Study personnel will screen all subjects for study eligibility based upon inclusion/ exclusion criteria listed in section 5 of this protocol. Subjects clearing all screening evaluations will undergo a graded exercise test on an arm ergometer (SCI subjects) or an electronically braked cycle ergometer (CON) to provide cardiac clearance and establish peak exercise capacity. Participants will refrain from activity/alcohol/caffeine 12h prior to testing and perform a continuous GXT (LodeAngio isokinetic arm ergometer or Monark 829e cycle ergometer) at a constant 60 rpm propulsion rate. After 30 minutes of rest, subjects with paraplegia will begin cycling with an initial workload of 0 W and will be increased by 15 W every 3 min until the subject can no longer maintain the target propulsion rate or requests to stop. Subjects with tetraplegia will be challenged by transitional workloads of 5 W. Control subjects will begin cycling at 50 W and the workload will be increased by 35 W increments every 3 minutes until 150 W and then by 10-15 W increments every 3 minutes until exhaustion. Expired gases will be continuously collected in a Hans-Rudolph Softmask worn by the subject and analyzed by an open-circuit indirect calorimetry system (Vmax229, Viasys, Inc.) with 12-lead EKG (Cardiosoft) rhythm detection. The ECG detection will use a standard 12-lead electrode array following washing of the electrode sites on the skin with an alcohol swab. Exercise termination will be consistent with the ACSM Guidelines for Exercise Testing and Training [9th Edition]. Indications for stopping the testing protocols in this research study include the following: 
 the onset of chest pain, or any drop in systolic blood pressure of 20 mm Hg, or an absence of increased systolic blood pressure with increased intensity of exercise, or a rise in blood pressure greater than 260 mm Hg for systolic pressure and greater than 115 mm Hg for diastolic pressure, or if the participant experiences any combination of these signs and symptoms: lightheadedness, confusion, nausea, cold skin, clammy skin, pale skin, blue skin, lack of muscle coordination, or an absence of increased heart rate with increased intensity of exercise, or noticeable abnormal changes in heart rhythm, or participant requests to stop the testing protocol, or signs and symptoms of severe fatigue, or

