Participants will receive intermittent exposure to moderate hypoxia (AIH) (HYP-123; Hypoxico Inc, New York, NY) under resting conditions. IH treatment will take place over a period of 4 consecutive days involving daily (Monday-Friday,) hour long sessions of alternating 6-minute hypoxic intervals ($\text{FIO}_2 = 0.09-0.12$) with 3-minute normoxic intervals ($\text{FIO}_2 = 0.21$). During hypoxic intervals, oxygen concentration may be adjusted to maintain participants SpO_2 levels between 75-90% (as previously described in IRB approved protocol #20150117). SHAM protocol will be the same as described above with $\text{FIO}_2 = 0.21$ at all times.

Blood oxygen concentration (SpO_2) will be continuously monitored with a pulse oximeter to ensure that participants do not fall below 75%. The following will also be monitored during and after hypoxia treatments: headaches, pain, lightheadedness, dizziness, altered vision, respiratory distress, cyanosis, spasms, autonomic dysreflexia or change in function.

4. On day 1 and day 4 of each treatment series, subjects will undergo a fasted OGTT (as described below #5.). On day 1, the OGTT will be performed before the treatment and on day 4 it will be performed after the treatment. Each treatment series will be followed by a repeat of the graded exercise tests within 24 hours of the final exposure session as described in Section 10.3 of this document.

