13.	
Provisions to Monitor the Data to Ensure the Safety of Subjects
 
a) Participants will be screened and approved for study participation by a physician boarded in physical medicine and rehabilitation.
 
b) Blood oxygen concentration (SpO₂) will be continuously monitored during the study treatments with a pulse oximeter to ensure that participants do not fall below 75%.
 
c) We will monitor for the following both during and for 15 minutes (or until cardiovascular responses return to baseline) after treatments: headaches, pain, lightheadedness, dizziness, altered vision, respiratory distress, cyanosis, spasms, autonomic dysreflexia or change in function. We will also monitor cardiovascular responses to treatment to ensure that participants do not exceed heart rate < 40 bpm or > 180 bpm, systolic blood pressure levels < 85 mm Hg or > 160 mm.
 
d) Testing is being performed at a medical center that is located near an emergency room.
 
e) Security personnel who staff the LPLC are “first responders”, and we have standing policies and procedures for emergencies in the Center (outlined in supporting documents). All lab staff hold current CPR certificates.
 
g) All adverse events – ‘serious’ or ‘not serious’- will be reported to the IRB within the mandated time period. For any adverse event the PI will immediately notify and consult with the Study Physician, and come to an opinion as the relatedness of the event and the study procedures as described in the protocol.
 
Adverse events will be evaluated by the Study Physician using the following criteria:
 
Grade 1, Mild: Awareness of symptom, but easily tolerated; usually transient requiring no special treatment; does not interfere with usual status or daily activities
 
Grade 2, Moderate: May be ameliorated by simple therapeutic measures; may interfere with, but not keep the participant from performing usual daily care or participating in daily activities.
 
Grade 3: Incapacitating event, inability to perform usual activities
 
Grade 4, Life-threatening/Disabling: Patient is at risk for death, or worsening disability or impairment as existed at the time of the event
 
For the first two grades the Investigators will observe the participant and as necessary institute standard medical or therapeutic care. Repeated occurrence of Grade 1 and 2 events may be cause for notification of the IRB by the Investigators that stoppage is appropriate. The Investigators may take this action and the IRB will be so notified.
 
Grade 3 and 4 events will be individually evaluated. Any occurrence of Grade 3 and 4 events may be cause for notification of the IRB by the Investigators that stoppage is appropriate. The investigators may take this action and the IRB will be so notified. Otherwise, upon an IRB determination that the (S)AE was related to the protocol, the study will stop and undergo evaluation for continuation.

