14.	
Withdrawal of Subjects
 
Subjects may withdraw from the study without prejudice to medical treatment at the center or involvement in future studies. The ICF advises students and employees of the rights with respect to study withdrawal.
 
We may end a subject’s participation in the study if s/he experiences any of the following adverse effects as a result of assessment and/or treatment: headaches, pain, lightheadedness, dizziness, altered vision, respiratory distress, cyanosis, muscle spasms, autonomic dysreflexia or change in function. We will also monitor cardiovascular responses, and discharge any subject whose responses are not in accordance with Guidelines for Graded Exercise and Testing of the American College of Sports Medicine (9th Edition).

15.	Risks to Subjects
	
Cardiovascular Morbidity and Mortality: Morbidity risks occur in 1/10,000 cases of intense cardiac exercise, and mortality occurs in 1/30,000 cases. Participants may find the exercise test exhausting, and may remain tired for the rest of the day. There is a risk of injuring the shoulders during intense arm cranking, which may make daily activities more difficult to perform. The mask placed over the mouth and nose for metabolic analysis may feel confining to some subjects, although it is flow-rated to 120 L/min and thus does not restrict breathing during exercise.
 
Risks of exposure to prolonged or chronic intermittent hypoxia include hypertension, heart attack and stroke.
 
Adhesive Allergy: Some individuals may experience brief, minor skin irritation or redness where the Cardiosoft ECG electrodes are placed. When occurring this is transient and typically goes away within several hours.
 
The risks of blood drawing include: fainting, the occurrence of temporary discomfort and/or bruise at the site of puncture; rarely, infection or the formation of a small clot or swelling to the vein and surrounding area may occur. There may be slight discomfort in the arm or hand during the inserting of the catheter into the vein. Occasionally, a small accumulation of blood (hematoma) may form at the point of insertion of the catheter. This may result in a small lump that will disappear. Occasionally, a small amount of bleeding may occur around the catheter site. On rare occasions, a local infection may occur around the catheter site.

16.	Potential Direct Benefit to Subjects
	Direct benefits are not anticipated.
17.	Vulnerable Populations

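### Section 5 admits resting systolic pressure up to 180 mm Hg, above the 160 mm Hg limit that section 13(c) sets for sessions given at rest, and no action is tied to that limit

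*Combined protocol and SAP*

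**What the plan says.** Four parts of the protocol bear on this point.

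- **Entry (section 5).** The systolic exclusion, for SCI and control subjects alike, is "Resting systolic blood pressure > 180 mm Hg". Diastolic pressure above 100 mm Hg and a resting heart rate of 120 bpm or more also exclude. There is no lower limit for systolic pressure or heart rate.
- **Treatment (section 10, step 3).** AIH is given "under resting conditions", and SHAM is the same procedure on room-air oxygen throughout.
- **Session monitoring (section 13(c)).** Cardiovascular responses are monitored so that heart rate does not go below 40 or above 180 bpm and participants do not reach "systolic blood pressure levels < 85 mm Hg or > 160 mm". Monitoring runs through the session and for 15 minutes afterwards, or until responses are back at baseline. What staff should do when a limit is passed is not stated.
- **Actions stated elsewhere.** Section 14 says the team will "discharge any subject whose responses are not in accordance with Guidelines for Graded Exercise and Testing" of an outside body. Section 10, step 2, stops the graded exercise test for, among other things, "a rise in blood pressure greater than 260 mm Hg for systolic pressure". Section 13(g) says: "For any adverse event the PI will immediately notify and consult with the Study Physician". Section 13(a) has participants "screened and approved for study participation by a physician boarded in physical medicine and rehabilitation".

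**The concern.** An entry limit for a resting measurement would normally be at least as strict as the limit that applies later, also at rest, during treatment. Here the order is reversed. Someone who screens at 170 mm Hg passes section 5 and then sits for a first session already above the section 13(c) figure, without having breathed any hypoxic gas.

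What is at stake is participant safety and uniform conduct. Staff who see 170 mm Hg before a session have a number but no instruction: they may treat outside section 13(c), or withhold treatment from an eligible participant without a written rule. Section 16 expects no direct benefit to participants, which is a reason to let the stricter of the sponsor's own two numbers decide.

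**Working it through.** The protocol reports no derived figure to reproduce. The check is a comparison of stated thresholds.

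**1. Do both limits describe the same state?** Section 5 refers to resting pressure. The section 13(c) limit covers treatment, and section 10, step 3, gives treatment at rest in both conditions. So both apply to a resting participant.

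**2. Is 160 really the exercise-test limit?** No. The exercise test has its own systolic stop at 260 mm Hg, and 260 - 160 = 100 mm Hg higher. Section 13(c) speaks of responses to treatment.

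**3. Is 160 a change from baseline?** No. It is written as a level. A participant at 170 mm Hg is over it with no response to treatment at all. The post-session wording adds a small ambiguity: with a baseline of 170, a participant could be back at baseline and still be above 160.

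**4. Entry and session limits side by side**

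- Systolic, upper: entry admits up to 180 mm Hg; session limit 160 mm Hg. Entry is looser by 180 - 160 = 20 mm Hg.
- Systolic, lower: entry has none; session limit 85 mm Hg.
- Heart rate, upper: entry admits below 120 bpm; session limit 180 bpm. Entry is stricter by 180 - 120 = 60 bpm, which is the expected order.
- Heart rate, lower: entry has none; session limit 40 bpm.

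The mismatch therefore has an explicit form at the upper systolic end, where two written numbers are in the wrong order. It has a milder form at the two lower ends, where entry is silent.

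**5. Does any written rule close the gap?**

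- Section 14 gives a discharge action, but its standard is an exercise-testing guideline and not 160 mm Hg. Section 10, step 2, refers to ACSM guidance for the exercise test ("Exercise termination will be consistent with the ACSM Guidelines for Exercise Testing and Training"), and the only systolic ceiling written there is 260 mm Hg.
- Section 13(g) requires consultation after an adverse event, but does not say that a reading above 160 is one.
- Physician approval under section 13(a) and the cardiac-clearance test in section 10, step 2, come before treatment and may catch such a person. Neither carries a resting criterion of 160 mm Hg.
- For contrast, the SpO2 range does have a stated control: section 10, step 3, lets oxygen concentration be adjusted to hold 75-90%.

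**6. Practical scale.** Each participant has 4 days x 2 conditions = 8 sessions, so 20 participants have 8 x 20 = 160 sessions. The documents do not say how many participants would rest above 160 and up to 180 mm Hg.

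**The case against.** The strongest reply is that the two limits do different jobs. Section 5 decides who enrols; section 13(c) governs what happens in a session. Both can be obeyed: a candidate at 170 mm Hg enrols and is then held at the session. This stands. A reader might infer that the protocol contradicts itself and cannot be followed, but the documents do not support that. What they show is an entry criterion that admits people the session limit would hold, with no statement that they are to be held.

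A second reply is that medical judgement already covers the case. Section 22 makes the study physician responsible for evaluating subjects and for all medical aspects of the study. That also stands, and it would be wrong to infer that nobody is in charge of the decision. But a general responsibility does not reconcile two written numbers. The diastolic exclusion may also narrow the affected group, without closing the systolic band.

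A third reply concerns the hazard. A reader might infer from section 15 that treating at 161-180 mm Hg exposes participants to a recognised risk of hypertension, heart attack and stroke. That section attaches those risks to prolonged or chronic intermittent hypoxia, whereas each series here is four sessions of about an hour. The documents do not say that the risks carry over, so the point rests on consistency and prudence, not on demonstrated harm.

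Finally, the documents give no rationale for either number, so preferring 160 is a judgement. It is the cautious one, and it uses a figure the sponsor has already chosen.

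**Conclusion.** The point holds as a minor safety-consistency correction. The size is a 20 mm Hg band, above 160 and up to 180 mm Hg, in which a participant is eligible on blood pressure but over the session limit at rest. A lesser gap of the same kind exists below 85 mm Hg and below 40 bpm.

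It rests on three assumptions: that the 160 figure, printed with an incomplete unit, is in mm Hg; that the section 13(c) figures are levels, as written; and that supporting documents not included here do not already supply a hold rule. The mismatch between the two numbers is certain from the text; its practical consequence is not, since the number of people affected may be zero of 20. Nothing here bears on the validity or precision of the AIH-SHAM comparison.

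**What to change.** 1. In section 5, change the resting systolic exclusion from above 180 to above 160 mm Hg.
2. In section 13(c), add that a session, AIH or SHAM alike, is not started, or is stopped and referred to the study physician, when systolic pressure is below 85 or above 160 mm Hg, or heart rate is below 40 or above 180 bpm. This covers participants who rest below the lower limits, so a separate entry floor is not essential.

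The same rule in both conditions keeps the rule itself from distinguishing AIH from SHAM.

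**Cost.** Two changes of wording, and a reading before each session: at most 160 readings for 20 participants, fewer if a baseline reading is already taken. Section 10 already names a pressure monitor. A few candidates may become ineligible. An occasional session may be held: one omitted session is 1/4 = 25% of that series' exposure, and a hold on day 4 would mean that the day-4 OGTT does not directly follow a treatment. Lowering the entry limit should make such holds less frequent.

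**Optional.** The sponsor may also wish to say whether a reading outside the limits is repeated after rest, whether a held session is omitted while the test dates stand, and that the number of sessions received (0-4) is recorded for each series. The mismatch does not require these rules.

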	We are not enrolling pregnant women, prisoners, persons under age 18, or cognitively impaired adults.
18.	Multi-Site Research
	NA
19.	Community-Based Participatory Research
	This project does not involve community based participatory research.
20.	Sharing of Results with Subjects
	Study outcomes for individual and group results will be shared with study participants upon completion of the study.
21.	Setting
	Procedures described in section 5. Procedures Involved will be completed in the Lois Pope Life Center on the Miller School of Medicine Medical Campus. Blood samples will be analyzed in the Clinical Biochemistry Lab or the DRI (3 rd Floor).
22.	Resources Available
	=Study Personnel =

[name] is a Professor in the in the Department of Neurological Surgery and Rehabilitation Medicine, and a Principal Investigator (Applied Physiology Research) for the Miami Project. He will serve as a Principal Investigator on the protocol and assessments, and will assist with data interpretation and dissemination.

[name], is an Associate Professor in the Department of Rehabilitation Medicine, who is boarded in Rehabilitation Medicine. He will conduct physician evaluations of study subjects and be notified of any (S)AEs. He will be responsible for all medical aspects of the study, injuries, and participant care.

[name] is a Post-doctoral Associate at the Miami Project to Cure paralysis. She will be responsible for recruiting and consenting participants. She will schedule participants for visits, and oversee all assessments.

[name], is a Research Associate Professor of Medicine and Director of the Clinical Biochemistry Lab of the DRI. He will assay all bloods for glucose and insulin and provide source data for the study on these analytes.

Other Resources:

As the target recruitment 6 per group, we are confident that this level of enrollment can be satisfied with our planned recruitment methods. The Miami Project maintains a database of persons who have volunteered their participation in research studies. This is a searchable database under the management of [name]., Director of Education. The Miami Project also maintains a database of individuals who have participated in past studies and volunteered additional participation.

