	Consent will take place in the Lois Pope Life Center on the University of Miami Miller School of Medicine Medical Campus. We will abide all regulatory mandates and suggestions of the FDA 'A Guide to Informed Consent - Information Sheet' www.fda.gov/RegulatoryInformation/Guidances/ucm126431.htm Before signing the ICF study subject candidates will be encouraged to share the ICF with family, a trusted family friend, their physician, or a member of the clergy. Candidates invited to the center will be required to read the approved consent form, and sign in the presence of a witness. The person obtaining consent will ask several questions to assure they understand the study procedures and risks. A statement on the consent form will advise university employees that their participation (or failure to participate) will not affect their employment or academic status. The statement in the consent will advise individuals with spinal cord injury that their participation (or decision to not participate) will not influence their treatment or candidacy for other studies in any way. Individuals will be given the right to stop the exercise test and may withdraw at any time without prejudice.

	Subjects will be presented with and asked to review the consent form. They will be queried whether they have any questions and if so, these questions will be addressed by the principal investigator. Once the consent form is signed, witnessed and signed by the principal investigator (or other person obtaining consent) a copy of the consent will be provided so that the subject can review their rights.
31.	Process to Document Consent in Writing See consent process in section 30. Consent Process
32.	Drugs and Devices This project does not involve drugs. The device used in protocol # 20160818 (HYP 123 Hypoxic Generator) has been used for the same purpose in previously approved protocols #20150117 and 20160337.

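### Exclusion h specifies a pregnancy test only for sexually active women, so Section 5 screening alone does not secure Section 17's unqualified statement that no pregnant women are enrolled

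*Combined protocol and SAP*

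**What the plan says.** Section 17 (Vulnerable Populations) is a flat statement: "We are not enrolling pregnant women, prisoners, persons under age 18, or cognitively impaired adults".

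Section 5 (Inclusion and Exclusion Criteria) admits "Males and females aged 18-60 years". Its exclusions a to h apply to both the spinal cord injury and the control group. The last of them, h, is "Pregnancy determined by urine testing in sexually active females". No exclusion or inclusion criterion mentions cognition or prisoners.

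Section 10 (Procedures Involved, Protocol item 1) names the working list: "Study personnel will screen all subjects for study eligibility based upon inclusion/ exclusion criteria listed in section 5 of this protocol". It does not refer to Section 17.

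Two other steps stand between a candidate and enrolment. Section 13, item a, says "Participants will be screened and approved for study participation by a physician boarded in physical medicine and rehabilitation". Section 30 (Consent Process) says "The person obtaining consent will ask several questions to assure they understand the study procedures and risks".

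**The concern.** Section 17 promises a result, that no pregnant woman is enrolled. Exclusion h is the only place that says how pregnancy is detected, and it limits the test to a subgroup. The subgroup is not defined: no look-back period is given, and no method for deciding who belongs to it. A woman whose pregnancy is unrecognised and who is not placed in that subgroup meets every listed criterion, because nothing on the list would reveal the pregnancy.

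She would then do graded exercise tests carried to exhaustion or until she could not keep going, and sit through four daily sessions breathing gas with an inspired oxygen fraction of 0.09 to 0.12. Section 16 anticipates no direct benefit to participants. The stake is participant protection. The trial's estimates and error rates are not affected.

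**Working it through.** The plan gives no figure on this point to reproduce. The check sets the four groups in Section 17 against the Section 5 list that Section 10 uses.

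- **Persons under 18:** fully carried over by the age range 18 to 60.
- **Pregnant women:** carried over as exclusion h, but with a test specified only for sexually active women.
- **Cognitively impaired adults:** not on the Section 5 list.
- **Prisoners:** not on the Section 5 list.

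**Pregnancy, step by step.**

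1. A woman known to be pregnant is ineligible under both sections, so there is no conflict there.
2. A woman with an unrecognised pregnancy who is classed as sexually active is tested under h and found.
3. A woman with an unrecognised pregnancy who is not so classed has no specified test. The telephone or personal pre-screen in Section 5 covers age and body size only, and the content of the physician's screen in Section 13 is not described.

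Only the third case separates what Section 17 states from what Section 5 delivers.

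**Number affected.** It is the number of female candidates not classed as sexually active who are in fact pregnant. The documents give neither the split by sex nor either proportion. The accrual target is 10 + 10 = 20, so among those enrolled it lies between 0 and 20, and nothing in the documents narrows that.

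**Planned exposure, for context.** Section 10 sets sessions of about 60 minutes in which 6 minutes of hypoxia alternate with 3 minutes of normoxia, on 4 days. One cycle lasts 6 + 3 = 9 minutes.

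- Six complete cycles take 6 × 9 = 54 minutes and contain 6 × 6 = 36 minutes of hypoxia. Over 4 days this is 36 × 4 = 144 minutes.
- If the session opens with hypoxia and the last 6 minutes are used as well, there are 7 × 6 = 42 minutes a day. Over 4 days this is 42 × 4 = 168 minutes.

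So a series contains 144 to 168 minutes of hypoxic gas. That is the planned exposure of any participant in the AIH series. It does not measure the size of the gap.

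**The case against.** The strongest reply is that the protocol already excludes pregnancy twice, in Sections 5 and 17, and that a physician who approves every participant and, under Section 22, answers for all medical aspects of the study would not let a pregnant woman through. This stands in part. The two sections do agree on eligibility, and physician approval makes a wrong enrolment less likely. It does not supply a test for an unrecognised pregnancy, because what the physician checks is not stated and the only stated test carries the filter. The consent form is not in the text reviewed, so it may say more.

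A reader might infer several stronger things that the documents do not support.

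- **That sexual activity is self-declared.** Section 5 uses the idea of self-report only for cardiac history ("Self-reported history of unstable angina or myocardial infarction within the previous month"). For sexual activity it is silent on the method.
- **That cognitively impaired adults can be enrolled under the protocol as written.** Section 17 is itself a restriction and bars them, a physician approves each participant, and the questions in Section 30 are asked so that understanding is assured. The absence of a pass mark is missing detail. It does not permit enrolling someone who fails to understand.
- **That safety monitoring rests mainly on reported symptoms.** Oxygen saturation is monitored continuously, heart rate and systolic pressure have limits in Section 13, and staff can see signs such as cyanosis or respiratory distress.

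**Conclusion.** The point holds for how pregnancy is ascertained. Section 5 screening, taken alone, does not secure what Section 17 states, because the one specified test is confined to a subgroup whose definition is not given. It does not hold as a claim that Sections 5 and 17 contradict each other on eligibility, or that the protocol allows pregnant or cognitively impaired people to be enrolled.

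The size is unknown and probably small in a trial of 20; that judgement is mine and does not rest on a figure in the documents. The conclusion assumes that the physician's screen adds no pregnancy test of its own and that the consent form does not widen exclusion h. It concerns who is tested at entry, not the timing of the test. The change is worth making because it touches a stated safety rule and costs almost nothing.

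The absence of cognitively impaired adults and prisoners from Section 5 is a matter of consistency between sections and no more.

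**What to change.** Reconcile exclusion h with Section 17 by removing the sexual-activity filter, so that the urine test already in the protocol is done in every female candidate who could be pregnant. The investigators should state in Section 5 which candidates that covers.

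As a consistency edit, add cognitively impaired adults and prisoners to the Section 5 exclusions in the same terms as Section 17, so that the list used for screening carries all four groups. A narrower phrase for cognitive impairment would leave the two sections still differing.

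The cost is a few extra test strips, a few lines of text, and possibly one candidate turned away. Nothing in the design or analysis changes.
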